In Malaysia, there are no specific guideline for prediabetes individual and they are managed according to the latest Clinical Practice Guideline in Malaysia (MOH *et al.*, 2020). For prevention prediabetes to further develop to diabetes, lifestyle intervention such as weight loss (5-10% of initial body weight), regular physical activity (150 min/week), with dietary strategies including reduced calories and behavior modification are recommended in Clinical Practice Guideline in Malaysia (MOH *et al.*, 2020). A high fibre diet (20-30g/day with 5 to 7 servings/day) consisting of vegetables, fruits, legumes and whole grains is encouraged too (MDES, 2020). All the prediabetic individuals will be referred to dietitian and nurse educators for 6 months routine treatment, prior to T2DM diagnosis, determined by second-round of oral glucose tolerance test (OGTT) in 6-month period (MOH *et al.*, 2020). To the puzzlement of many diabetes researchers and clinicians, some of the prediabetes cases showed tremendous improvement in their blood sugar result, yet some of the prediabetes

individuals developed full-blown of T2DM with their blood sugar result higher than the normal range; despite all of them followed the same routine treatment from healthcare clinics. Perhaps, besides the usual routine treatment from Clinical Practice Guideline (MOH *et al.*, 2020) (weight management, physical activity advices and dietary modification); prediabetic individuals who able to improve their blood sugar result in 6-month period has particular meal-timing, compared to those has uncontrolled blood sugar result in 6-month period.

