research assistant using the following questionnaire including (1) Munich Chronotype Questionnaires (MCTQ) (Appendix D), (2) Pittsburgh Sleep Quality Index Questionnaire (PSQI) (Appendix H), (3) Harvard Light Exposure Questionnaire (HLEQ) (Appendix G), (4) International Physical Activity Questionnaire (IPAQ) (Appendix C) and (5) Chrononutrition Profile Questionnaire (CPQ) (Appendix I). Anthropometry measurements including body fat, height, body fat percentage, visceral fat, waist circumference and hip circumference will be measured. Participants are requested to fill up 3-days dietary record (3DDR) (2 weekdays and one weekend day) and the data will be collected in the next visit. Baseline reading of fasting plasma glucose (FPG, OGTT, liver function, and HbA1c) will be retrieved from medical records in the community clinic. Routine treatment will be provided as usual. To minimize the loss of follow-up, phone conversations will be made to ensure the 3-days dietary data is completed.

At the second visit (three months from the baseline), all participants are required to wear a CGMS sensor at the back of their upper arms to measure the 24 hours glucose fluctuation over 14 consecutive days. 3DDR will be given to participants to record their consecutive 3 days dietary record and will be returned after 14 days. After 14 days, participants will return the CGMS sensor at the community clinic. Or alternative way of CGMS sensor collection by an assistant at the participant's home. All questionnaires will be interviewed by a trained research assistant again. Anthropometry measurements including body fat, height, body fat percentage, visceral fat, waist circumference and hip circumference will be measured repeatedly.

At the third visit (six months from the first visit), for FBG, OGTT and HbA1c test, all the readings will be retrieved by the research assistant from the medical record to document the glycemic outcome. The participants will be interviewed by the trained research assistant during all clinic visits using similar questionnaires. All anthropometry measurements (body fat, height, body fat percentage, visceral fat, waist circumference and hip circumference) will be conducted again. 3DDR will be given to record their 3 days dietary intake again and the record progress will be followed up through phone. The original 3DDR will be collected at the routine appointment.

Sample size Calculation:

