The FreeStyle Libre Pro CGM system consists of a disposable sensor, an applicator, and a reader; that is used to start the sensor on the participant and gather the glucose data at the end of the CGMS period. The Sensor can be worn for up to 14 days, on the back of their upper arm (Figure 7). Once applied, a sensor will measure and store glucose readings every 15 minutes. The 24-hour CGMS does not require any participant action as calibration for the sensor is not needed. Readings from the 24-hour CGMS will not be made available to participants in real time, hence, it will prevent the bias that may arise from unmasked real-time glucose readings. The data from all the 24-hour CGMS (Freestyle Libre Pro, Abbott, Germany) sensors is easily accessible through the FreeStyle Libre Pro Software or The LibreView Cloud. In the present study, the 24-hour CGMS reading will be taken 14-day prior to second visit/second-round OGTT reading. All the data from 24-hour CGMS will be analyzed to

investigate to obtain the optimal-meal-timing. The 24-hour CGMS data will be match with 3-day food diary too.

Exposure measures Meal-timing and chrononutrition

At the baseline visit, the researcher will guide the participants to fill out the 3-day food diary covering two weekdays and one weekend day (consecutive Sunday-Tuesday or Thursday-Saturday). Three-day food diary will be taken twice in the entire study. At the baseline visit, 3-day food diary will be interviewed by researcher to the participants. This food diary data will be served as baseline meal-timing data. Subsequently, participant will be given another 3-days daily dietary at second visit, 14-day prior to third visit. Participants are required to record the time, type, description and number of foods and beverages consumed throughout the day. Brand information, ingredients and cooking method will be recorded where applicable, particularly for home-cooked food. Pictures of household measuring utensils and various food portion sizes are printed in the food diary to assist participants in quantifying their food intake. For 14 day return the CGMS, researcher will be interviewed participants on the completeness of 3 days daily dietary intake.

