Energy and macronutrients analysis of dietary record will be performed using Nutritionist ProTM (Axxya Systems, Stafford, TX, USA), based principally on the Nutrient Composition of Malaysian Food and the food product labels. Energy intake will be compared with estimated basal metabolic rate (BMR) to exclude participants who are under-reporting or overreporting their energy intake in their 3-day food diary. BMR is calculated using standard equations based on sex and age provided by FAO/WHO/UNU (1985) (FAO/WHO/UNU 1985). For participants in a non-dieting population, Torun et al. (1996) proposed that a ratio between energy intake and BMR of less than 1.39 and more than 2.24 be considered as under-reporting and over-reporting respectively. These cut-off points will be applied in the present trial. From the 3-day food diary data, The investigator will investigate the dietary intake as reported on the second day of recording. The second day will be selected over the first one to ensure that participants have also include night-time eating in the records. Compare to the later days, which may have been burdened by increasing exhaustion related to the record-keeping, the second day better represents the habitual dietary intake (Ahola et al. 2019). To investigate the energy and macronutrient intakes over the course of the day, five periods will be performed as follows: night (from 00:00 to 04:49), morning (from 05:00 to 09:59), midday (from 10:00 to 13:59), afternoon (from 14:00 to 16:59) and evening (from 17:00 to 23:59), adapted from Ahola et al. (2019). As these periods differed in their duration, energy intake per hour will also be calculated for each of the five periods. In addition, energy and macronutrient intakes per hour (e.g. intakes reported between 10:00 and 10:59 contributed towards the hour "10:00"). Diet quality will be derived from a 177 food items FFQ at second visit, where the Healthy Eating Index (HEI) will be calculated. This FFQ is adapted from the FFQ used by the Malaysian Adults Nutrition Survey (MANS) 2014 (IPH 2014) (Appendix C). Participants will be required to indicate frequency of foods consumed in the last 1 month. Individual portion size will be asked for each food, and pictures of the various portion size will be

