pattern from the validated questionnaires PSIQ and light exposure from the validated questionnaire HLEQ.

Statistical Analysis

All data will be performed statistical analysis using the SPSS software version 20 (SPSS Inc., Chicago, IL, USA). The socio-demographic will be presented as mean, standard deviations, median, interquartile range, frequency, and percentage. Data cleaning will be performed to exclude the outlier data before the normality is checked using Kolmogorov-Smirnov Test. The investigator considered $p < 0.05$ to be statistically significant. Chronotype, sleep quality, and light exposure will be analyzed as categorical variables whereas dietary intake, chrononutrition, anthropometry, glycemic measure, and physical activity will be analyzed as continuous variables.

The investigator will perform a multivariable generalized linear model to examine the association between night meal pattern (last night mealtime either dinner or supper with calories intake, frequency of night snacking, and the total number of the night snacking) and glycemic outcome (HbA1c, FPG, 2hPPG, CGM profile) by adjusting for the potential covariates. Specifically, nighttime will be characterized by the time range from 1900 and 0659 hours based on Malaysia solar time. The investigator will explore the late-night meal timing in 2000, 2100, and 2200 to examine its association with glycemic outcomes. The potential confounders include sociodemographic characteristics, physical activity, sleep pattern, sedentary behavior, diet quality, and light exposure will be controlled. ANCOVA test will be performed to understand the association between chrononutrition (breakfast skipping, meal frequency, eating window, sleep timing, chronotype, and fasting pattern) with glycemic variables, controlling for potential covariates (sociodemographic characteristics, light exposure, diet quality, physical activity and sleep pattern).

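### The only diet-quality score with a stated instrument and visit is taken about three months into dietitian care, so in models of baseline exposure against 6-month change it adjusts for a post-baseline value

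*Combined protocol and SAP*

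**What the plan says.** **Role of diet quality.** The Statistical Analysis section names diet quality among the confounders in the generalized linear model for night meal pattern. It does so again in the ANCOVA for chrononutrition and chronotype, "controlling for potential covariates (sociodemographic characteristics, light exposure, diet quality, physical activity and sleep pattern". It does not say which visit supplies the exposure or the covariates.

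**Instrument and timing.** Under the exposure measures in section 3: "Diet quality will be derived from a 177 food items FFQ at second visit, where the Healthy Eating Index (HEI) will be calculated". The recall window follows: "Participants will be required to indicate frequency of foods consumed in the last 1 month".

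**When the second visit falls.** The visit narrative says: "At the second visit (three months from the baseline), all participants are required to wear a CGMS sensor". The CGM description differs, saying that "the 24-hour CGMS reading will be taken 14-day prior to second visit/second-round OGTT reading". The Introduction puts the second OGTT in the 6-month period.

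**Care in the meantime.** The Introduction states: "All the prediabetic individuals will be referred to dietitian and nurse educators for 6 months routine treatment". Of the guideline's lifestyle advice it says weight loss and exercise "with dietary strategies including reduced calories and behavior modification are recommended".

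**Other covariates.** Section 3 gives the physical activity, sedentary behaviour, sleep and light exposure questionnaires at the first visit.

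**Where the food-frequency questionnaire (FFQ) is missing.** The baseline interview list begins "using the following questionnaire including (1) Munich Chronotype Questionnaires (MCTQ) (Appendix D" and goes on to PSQI, HLEQ, IPAQ and CPQ. The second visit repeats the questionnaires. Neither this narrative nor Table 4 mentions an FFQ or the HEI. The FFQ is referenced to Appendix C, which holds the physical activity questionnaire.

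**The concern.** A confounder should describe the participant before the exposure has had time to act on it and before the outcome changes. Three of the four main outcomes (HbA1c, FPG and 2-hour glucose) are changes from baseline to 6 months. If the exposure is baseline chronotype or meal timing, a diet score covering roughly months 2 to 3 lies between exposure and outcome. It has also been shaped by dietitian care directed at diet.

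Two errors can follow, and they pull in different directions. If late eating leads to poorer diet later, adjusting for later diet removes part of the effect being estimated. If it does not, the later score is only a noisy stand-in for baseline diet and leaves confounding behind. Since the study exists to estimate these associations, either error reaches its main conclusions.

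There is a practical risk as well. A site working from the visit narrative or Table 4 could omit the questionnaire, and an analyst could build diet quality in more than one way.

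**Working it through.** **1. Plan's own figure.** The plan gives no figure on this point. The sample-size calculation is not affected.

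**2. The descriptions of diet quality side by side.**

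| Place | What diet quality is | When available |
|---|---|---|
| Exposure measures, section 3 | HEI from a 177-item FFQ, 1-month recall | Second visit only |
| HEI scoring formula, same section | Food-group servings taken from the participant's diet record | 3-day record, taken at baseline and again later |
| Statistical Analysis, lifestyle-factor model | Distribution of energy, carbohydrate, protein and fat | Derived from the 3-day record, as above |

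Only the first row gives both an instrument and a visit. The adjustment sentences do not say which row they mean.

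**3. Timeline.** Recruitment is at the first diet-clinic visit, and routine care runs for 6 months. Month 3 less a 1-month recall covers months 2 to 3. If the second visit is instead tied to the second OGTT, the score is later still. It is post-baseline on both readings.

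**4. Which analyses are affected.**
- Baseline exposure with change to 6 months in HbA1c, FPG or 2-hour glucose: the score falls after exposure and before outcome. Affected.
- Second-visit meal timing with second-visit CGM: the score is roughly contemporaneous. Defensible.

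**5. Direction of bias: an illustration.** All values here are assumptions, none an estimate from the documents. Let X be baseline lateness of eating, D0 and D3 diet quality at baseline and month 3, and Y the glycaemic outcome, with X, D0 and D3 standardised.

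D3 = s·D0 + m·X + error; Y = b·X + g0·D0 + g3·D3 + error; corr(X, D0) = r.

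Assume b = 0.13, g0 = g3 = −0.2, r = −0.3. Let the stability of diet s run from 0.3 to 0.7 and the effect of X on later diet m from 0 to −0.4.

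- True total effect = b + g3·m.
- With c = m + s·r and k = s + m·r: cov(X,Y) = b + g0·r + g3·c, and cov(D3,Y) = b·c + g0·k + g3.
- Coefficient of X adjusted for D3 only = [cov(X,Y) − c·cov(D3,Y)] / (1 − c²).

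Example with s = 0.5, m = 0: c = −0.15, k = 0.5. Then cov(X,Y) = 0.13 + 0.06 + 0.03 = 0.22, and cov(D3,Y) = −0.0195 − 0.1 − 0.2 = −0.3195. The coefficient is (0.22 − 0.0479) / 0.9775 = 0.176, against a true 0.130.

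| s | m | True total effect | Adjusted for D0 | Adjusted for D3 only |
|---|---|---|---|---|
| 0.3 | 0 | 0.130 | 0.130 | 0.185 |
| 0.5 | 0 | 0.130 | 0.130 | 0.176 |
| 0.7 | 0 | 0.130 | 0.130 | 0.162 |
| 0.3 | −0.2 | 0.170 | 0.170 | 0.173 |
| 0.5 | −0.2 | 0.170 | 0.170 | 0.154 |
| 0.7 | −0.2 | 0.170 | 0.170 | 0.127 |
| 0.3 | −0.4 | 0.210 | 0.210 | 0.155 |
| 0.5 | −0.4 | 0.210 | 0.210 | 0.118 |
| 0.7 | −0.4 | 0.210 | 0.210 | 0.066 |

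Without mediation, the month-3 adjustment overstates the effect by 0.032 to 0.055. With the strongest mediation assumed, it understates it by 0.055 to 0.144. Baseline adjustment recovers the true value throughout.

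**The case against.** The best defence is that the plan does not commit itself to a month-3 score. The HEI formula and the lifestyle-factor model both point to the 3-day record, which exists at baseline. A reader might infer that diet quality is measured only once and cannot serve as a confounder; the documents do not support that, because a baseline diet measure may be available. This stands and limits the point. It does not remove it: an energy and macronutrient distribution is not the HEI, and the HEI formula follows directly on the FFQ description. The plan analyses only the second day of the record. The visit narrative has the baseline record completed after the visit and collected at the next one, while the exposure section has it taken by interview at baseline.

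Second, this is an observational cohort in which everyone receives routine care, so the test is whether the covariate precedes the exposure and the outcome change, not whether it precedes treatment. That is right. It is why the point is confined to baseline exposure against 6-month change and does not extend to second-visit CGM analyses.

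Third, a reader might infer from the visit narrative and Table 4 that the FFQ is never given. That goes too far. The exposure section does instruct its use, the narrative's list is not worded as exhaustive, and the sedentary-behaviour questionnaire is also missing from both places although it is administered. Figure 3 is not shown and no Appendix F appears in the text supplied. What can be shown is an omission from two places and a wrong appendix reference.

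Fourth, it is tempting to turn the 50% dropout allowance into a count of people lost to the adjusted models for want of a month-3 score. The documents do not support such a count. The allowance also covers non-response and non-compliance, most people lost by 6 months would lack the outcome too, and no missing-data method is stated.

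**Conclusion.** The point holds for models relating baseline chronotype or meal timing to change to 6 months in HbA1c, FPG and 2-hour glucose. There, the only diet-quality score with a stated instrument and visit is post-baseline, possibly a mediator, and a poor proxy for the diet the participant brought to the study. The bias can go in either direction. Its size cannot be derived from the documents, and the illustration shows direction under assumed correlations only.

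The conclusion rests on two readings: that the adjustment sentences mean the FFQ-based HEI, and that the exposure in these models is the baseline one. The plan states neither, and that silence is part of the defect. The three descriptions of diet quality and the mismatch between the exposure section, visit narrative, Table 4 and appendix reference need reconciling whichever reading was intended.

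**What to change.** - Give the FFQ at the baseline visit. Its 1-month recall then describes diet largely before counselling, even if the dietitian is seen the same day. Add it to the visit narrative and to Table 4 at baseline, and correct the appendix reference.
- State one definition of diet quality and use it in the exposure section, the HEI formula and the Statistical Analysis section.
- For each model, name the visit that supplies the exposure and the covariates. Use baseline diet quality where baseline exposure is related to 6-month change.
- Keep any second-visit HEI for second-visit exposure with second-visit CGM, or report it descriptively.
- The document is dated 6 May 2024 and the research schedule ends third visits on 06/03/2024, so baseline FFQ data may no longer be obtainable. In that case, use a diet-quality measure from the baseline 3-day record, and say when that record was completed relative to the first dietitian contact.

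The cost is protocol and SAP wording and, where the FFQ can still be moved, a longer baseline interview. The fallback needs no new data collection but is a thinner measure than the FFQ.

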1.1 Prediabetes

Prediabetes is defined as a condition in which people have higher than normal blood glucose levels but not high enough for a diagnosis of diabetes. Prediabetes prevalence is higher than that of diabetes in China and many of the Western Pacific region countries, this is true of many countries in Asia (IDF 2017). South Asian population also have a high prevalence of prediabetes and a more rapid progression to diabetes (IDF 2017). In Malaysia, National Health and Morbidity Survey (IPH 2019) found the prevalence of prediabetes was 8.9%. These prevalence were likely to be underestimates because diagnosis relied only on a single fasting blood sugar, history of physician diagnosis and information on medication (Nanditha et al. 2016). Globally, an estimated 318 million people had prediabetes in 2015, with a projected alarming increase to 482 million in 2040 (IDF 2015). Prediabetes is high-risk condition for diabetes and cardiovascular disease (Nanditha et al. 2016). Without appropriate interventions, 5.8%-18.3% of people with prediabetes develop diabetes yearly (Anothaisintawee et al. 2017). How to prevent the development of diabetes from prediabetes?

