To investigate the association of physical activity (MET score and steps count), sedentary behaviors (MET score), sleep pattern (sleep duration), diet quality (distribution of total energy, carbohydrate, protein, and fat), and light exposure (timing responded to a different type of light) with glycemic outcome, the multivariable generalized linear model will be conducted. Meanwhile, anthropometric measures (body mass index, body fat, and waist circumference) will be categorized as either normal or overweight and obesity group, followed by using logistic regression to examine the association between anthropometry status and glycemic outcome (non-diabetes or diabetes). In addition, the glycemic outcome will be categorized into diabetes incidence (diabetes and non-diabetes) to determine the participants who had been diagnosed with diabetes at 6 months. A logistic regression test will be used to examine the association between early and late-night mealtime and diabetes incidence.

Quality control

To ensure that the database accurately reflects the data reported in the questionnaires, a pre-test will be carried out. The research assistant trained to conduct the study procedures included interviewing administrative questionnaires, CGMS device, 3 days dietary record, and pedometer. Monthly meetings are held with the principal

investigator to review study procedures and progression. A monthly report will be documented after the meeting.

Data monitoring and management

Participants are anonymized and assigned with a specific ID at study entry. To ensure accuracy and completeness of data entry, data are checked by identifying if there is any outlier or missing value. The data checking process is performed in the first, third and sixth month of the data collection, such that the experience gained can be used to train the research assistant for improvement. Paper documents are kept in a locked cabinet and electronic data are stored on password-protected computers which can only be accessed by research team members. All records will be kept for at least 5 years after completing the study. After 5 years, all papers will be shredded using an office shredder. Extra care should be taken with sensitive or confidential information and a secure paper destruction service bin used. Digital data will be destroyed by deleting or overwriting information and destroying the physical media, such as CD rom.

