4. PROPOSED RESEARCH SCHEDULE

Research Activities

[figure not shown]
Activities	Start Date	End Date
Systematic review. Research and methodology classes	07/09/2021	06/03/2022
Baseline recruitment, collection of FBS, anthropometric measurements and lifestyle habits; distribute 24- hour CGMS	07/03/2022	06/11/2022
Second visit, collection of FBS, anthropometric measurements and lifestyle habits; distribute 24-hour CGMS	07/11/2022	06/07/2023
Third visit, collection of FBS, anthropometric measurements, lifestyle habits and collect the 24-hour CGMS	07/07/2023	06/03/2024
data key in, data analyses to investigate the optimal-meal-timing, anthropometric measurements, lifestyle habits and the associations between these variables; publication	07/03/2024	06/09/2024

Milestones

Activities	Date	Cumulative Project Completion Percentage (%)
Completion of systematic review to study optimal-meal-timing, chrononutrition, lifestyle factors and	31/03/2022	10

anthropometric measurements in prediabetes individuals		
Baseline recruitment completed, by using convenient sampling method. OGTT, FBS and HbA1c traced from medical record. Anthropometric measurements and lifestyle habit information collected. 3- day food diary and CGMS distributed.	30/11/2022	35
Second visit completed. Anthropometric measurements and lifestyle habit information collected. 3-day food diary and CGMS distributed.	31/07/2023	60
Third visit completed. OGTT, FBS and HbA1c traced from medical record. Anthropometric measurements and lifestyle habit information collected. 3-day food diary and CGMS collected	31/03/2024	85
Data key in, data analyses and publication	31/08/2024	100

Gantt Chart of Research Activities with Milestones

5. References

hemoglobin A1c in prediabetes individuals. *The Journal of Biological and Medical Rhythm Research* 34(3): 393-402.

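### Outliers are to be excluded before analysis with no variable, cut-off or limit to verified errors, so genuine high 6-month glycaemic values can be deleted

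*Combined protocol and SAP*

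**What the plan says.** Section 3, Statistical Analysis, gives the whole rule in one sentence: "Data cleaning will be performed to exclude the outlier data before the normality is checked using Kolmogorov-Smirnov Test". The same paragraph lists glycaemic measures among the continuous variables, and nothing exempts them. No analysis with all values kept is planned.

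Outliers appear once more, under Data monitoring and management in Section 3. There, to secure accurate and complete entry, "data are checked by identifying if there is any outlier or missing value". That passage sets no comparison with the source and no rule for values that prove correct, and it does not refer back to the exclusion.

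The plan does give limits for another data-based exclusion. For the food diary it adopts a proposal that "a ratio between energy intake and BMR of less than 1.39 and more than 2.24 be considered as under-reporting and over-reporting respectively".

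It also expects true high values. Section 1 says that under the same routine care some prediabetes "individuals developed full-blown of T2DM with their blood sugar result higher than the normal range". Section 2, heading 1.1, says that without appropriate interventions "5.8%-18.3% of people with prediabetes develop diabetes yearly". Section 3 plans a logistic regression on diabetes at 6 months and takes the third-visit glucose and HbA1c readings from the clinic medical record.

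**The concern.** In a prediabetes cohort the highest 6-month readings are not noise. They belong to the people who progressed, and they carry much of the information on whether late eating goes with worse glycaemia. A rule that removes unusual values, and not only wrong ones, can remove exactly these people.

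Under the study hypothesis, three things follow. The slope on meal timing is pulled towards zero. The residual spread shrinks, so standard errors come out too small. The Kolmogorov-Smirnov check is then run on data already trimmed, so it says little about the data collected. Since no cut-off is set, it can also be chosen after the values have been seen.

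**Working it through.** **1. The plan's completer count.** Inputs from Sample size Calculation: effect 0.13, two-sided alpha 0.05, power 0.90. With 0.13 entered as f², the noncentrality is √(0.13 × 83) = √10.79 = 3.28 on 81 df (one predictor), and power is 0.901. So 83 reproduces, as does 83 / (1 − 0.5) = 166. The summary table at the front plans 120 participants; at the same 50% dropout, 120 × 0.5 = 60 complete.

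**2. Expected progressors.** Assume the yearly rate under heading 1.1 acts evenly over the year.

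- Lower: 1 − (1 − 0.058)^0.5 = 2.9%; × 83 = 2.4; × 60 = 1.8
- Upper: 1 − (1 − 0.183)^0.5 = 9.6%; × 83 = 8.0; × 60 = 5.8

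The counts may be lower, because the quoted rate is for people without appropriate interventions and participants receive routine care.

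**3. Where common rules would cut.** For normal data the 1.5×IQR upper limit is mean + 2.698 SD. Means are the midpoints of the prediabetes ranges in Tables 2 and 3; the SDs are assumed.

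| Measure | Mean | SD assumed | 1.5×IQR limit | 3-SD limit | Diabetes from |
|---|---|---|---|---|---|
| HbA1c, % | 5.9 | 0.2–0.35 | 6.44–6.84 | 6.50–6.95 | 6.3 |
| FPG, mmol/L | 6.5 | 0.4–0.7 | 7.58–8.39 | 7.70–8.60 | 7.0 |
| 2hPPG, mmol/L | 9.4 | 1–2 | 12.10–14.80 | 12.40–15.40 | 11.1 |

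Every limit lies inside the diabetic range. So an error-free value cut at the top belongs to someone in that range, while progressors between the diagnostic threshold and the limit are kept.

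**4. Effect on the slope, using the plan's effect size.** Simulated: 3,000 error-free datasets of 83 per setting, true correlation √(0.13/1.13) = 0.339, residuals normal or right-skewed (lognormal, sigma 0.6). High values are the top 2.9% or 9.6%; ranges cover both.

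| Residuals | Rule | High values removed per dataset | Slope lost | Power, full data | Power, trimmed |
|---|---|---|---|---|---|
| Normal | 3 SD | 0.1 | about 2% | 0.883–0.885 | 0.876–0.880 |
| Normal | 1.5×IQR | 0.4 | about 7% | 0.887–0.895 | 0.858–0.862 |
| Normal | 2 SD | 1.7–1.8 | about 20% | 0.891–0.893 | 0.784–0.792 |
| Skewed | 3 SD | 1.2–1.3 | 4–5% | 0.885–0.886 | 0.941–0.943 |
| Skewed | 1.5×IQR | 2.3–3.4 | about 9% | 0.882–0.886 | 0.959–0.965 |
| Skewed | 2 SD | 2.3–3.6 | 10–11% | 0.879–0.893 | 0.953–0.955 |

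The slope falls in every row, but power moves either way, so the significance of a result can turn on the rule chosen.

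**5. Effect when progressors form a distinct tail.** Simulated for HbA1c: N = 83, 2,000 replicates per setting, baseline uniform 5.6–6.2%, baseline-to-6-month correlation 0.5 or 0.7, about 2.5 or 7.9 progressors, gain 0.3, 0.5 or 0.8 points, odds of progression doubled per SD of meal time, rule 1.5×IQR or 3 SD. That makes 2 × 2 × 3 × 2 = 24 settings. The slope moved towards zero in all 24, by 4% to 96%, and the standard error was 0.63 to 0.99 of its full-data value. With a 0.3-point gain, only 0.15 to 0.8 progressors were removed per dataset. With the odds ratio set to 1, there was no systematic shift.

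**The case against.** The strongest reply is that the authors meant errors: outliers are otherwise mentioned only as a check on data entry. That may be so. But the analysis sentence says exclude, without that limit, and the data-entry passage neither restricts it nor protects confirmed values. If errors were meant, the fix only says so.

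The second reply is that the harm may be slight. This stands in part. Under a 3-SD rule with near-normal data, or with small gains, less than one progressor is lost per dataset. The count of 24 out of 24 also assumes an association between later meals and progression. It shows direction under the hypothesis, not size.

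Three stronger readings are tempting, and the documents do not support them.

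- A reader might infer that most progressors will be deleted. No cut-off is given, and common limits sit above the diagnostic thresholds, so many would stay.
- A reader might infer that progressors must also drop out of the diabetes-incidence model. That analysis refers to participants diagnosed by 6 months, which may be a recorded diagnosis that cleaning of continuous values does not touch. The model is affected only if status is derived from the cleaned values.
- A reader might infer that the data checks end too early to reach 6-month values, because "The data checking process is performed in the first, third and sixth month of the data collection" while the schedule opens the third-visit phase on 07/07/2023. The months may count from each participant's entry. That date is also hard to square with Section 3, which puts the third visit six months after the first, when recruitment opens in March 2022. Nothing here rests on it.

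**Conclusion.** The concern holds. As written, the rule permits removal of true high 6-month HbA1c, FPG or 2hPPG values, and the plan's own figures imply that a handful of participants (2.4 to 8.0 of 83, or 1.8 to 5.8 of 60) will reach the diabetic range. If later meals raise glycaemia, the bias is towards no association, with standard errors that are too small. No single size can be given. It runs from about 2% of the slope (3 SD, near-normal data) to most of it (1.5×IQR, large gains), and rests on assumed SDs, progression gains and distribution shape. If there is no association, the slope is not systematically shifted, so the rule should not be read as creating a false effect of meal timing. The sentence should be changed before the data are analysed, but it does not invalidate the design.

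A separate, minor matter: the summary table at the front defines the main outcomes as 6-month change, while Study Outcomes in Section 3 defines the glycaemic outcome, the term that the models use, as the measures themselves, without change. The conclusion above does not depend on which is meant.

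**What to change.** Replace the sentence with:

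> Values flagged as outliers are corrected or set to missing only if shown to be wrong against the source record (for glycaemic values, the clinic medical record); all other values are kept in the main analysis. Robust standard errors are used for the continuous-outcome models. Any outlier-excluded result, with its cut-off fixed before analysis, is a sensitivity analysis.

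State also that the source check covers all 6-month values. The energy-intake to BMR cut-offs for the food diary are a separate, stated rule and stay unchanged. A log transformation is not a general substitute: if the dependent variable is change, many values will be zero or negative.

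For the minor matter, reconcile the two outcome definitions and name one dependent variable and one primary model in advance. Any alternative change or baseline-adjusted model is then a sensitivity analysis.

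The cost is a few lines of wording and a look-up of flagged values in records that the team already consults. The downside is that a few true extreme values may widen the confidence intervals.
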